- 14 Cancer that is not considered cured, except basal cell or squamous cell carcinoma of the skin (cured defined as no evidence of cancer within the past 5 years)
- 15 Any serious medical condition that is likely to impede successful completion of the study, such as certain mental disorders, hypersensitivity to onabotulinumtoxinA or anesthetics used in the study, syncope
- 16 Daily use of a pad or device for incontinence required
- 17 Interested in future fertility
- 18 PVR greater than 350 ml
- 19 Serum prostate specific antigen level greater than 8 ng/ml (Hybritech). For those with a PSA between 4-8 ng/ml, the PSA elevation must be considered to

- be from a benign cause in the opinion of the PI. This decision can be based on PSA velocity, previous TRUS biopsy, percent free PSA, or other clinical estimations in keeping with sound urologic care
- 20 No alpha-blockers in the past 7 days before biopsy.
 - 21 Has taken phenylephrine, pseudoephedrine, imipramine, an anticholinergic, or cholinergic medication within the past 2 weeks
 - 22 Has taken estrogen, androgen, any drug producing androgen suppression, or anabolic steroids within the past 4 months
 - 23 Is taking aminoglycosides or any drug that interfere with neuromuscular transmission. Eaton-Lambert syndrome, hemophilia, hereditary clotting factors deficiency, or bleeding diathesis
 - 24 Must be off aspirin, NSAIDS, and Coumadin for 7 or more days prior to onabotulinumtoxinA injection
 - 25 Enrolled in another treatment trial for any disease within the past 30 days

VIII DESIGN

This Phase 2 clinical research trial is a double-blind, randomized, placebo-controlled, parallel-group study to compare the treatment effects of onaBoNT-A 200 U versus 0.4 mg per day of oral tamsulosin in male veterans diagnosed with moderate to severe LUTS (AUASS equal to or greater than 8) associated with BPH. A total of 74 volunteers will be recruited to participate in this clinical trial. Volunteers will include only males who are greater than 50 years of age and diagnosed with LUTS associated with BPH. They are veterans who visit the MEDVAMC. There are no eligibility restrictions as to race or ethnicity.

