Transition zone biopsies will be performed at Visit 2, 30 days before treatment, and again at 3 months post-treatment. A total of 6 biopsy cores (i.e. 3 cores from the left and right transition zone) will be obtained from each volunteer. Prostate biopsy cores will be rapidly snap frozen in liquid nitrogen in coded and labeled containers and sent to [name] laboratory located at University of Texas Health Science Center - Houston Medical School for further processing.

A Randomization

Volunteers will be randomized using a blocked randomization approach by the MEDVAMC Research Pharmacy to either: ARM 1: onaBoNT-A 200 U prostate injection and placebo oral capsule daily or ARM 2: Placebo prostate injection (saline) and tamsulosin 0.4 mg capsule daily. Subjects will be randomized into one of the two treatment arms, using a block size of 4. The order in which the treatments are assigned in each block is randomized and this process is repeated for consecutive blocks of subjects until all subjects are randomized. This process ensures that after every fourth randomized subject, the number of subjects in each treatment group is equal. The MEDVAMC will prepare both pills (i.e. tamsulosin and placebo pill) and injections (i.e. onaBoNT-A and placebo saline injection) so that the study subject, investigator and all personnel treating or evaluating the subject will be blinded to treatment allocation.

B Schedule Of Events During Treatment Protocol

Tests/Time	Visit 1: Screening	Visit 2: Biopsy	Visit 3: Injection (4 weeks Post- biopsy ± 3 days)	Visit 4: Telephone Visit (Day 3 Post Prostate Injection)	Visit 5: Telephone Visit (1 Week Post- Injection ± 3 days)	Visit 6: (4 Weeks Post- Injection ± 3 days)	Visit 7: End of Study (3 months Post Injection ± 3 days)
Physical with DRE	X						X
Medical History	X						
Vital signs	X	X	X			X	X
Flowrate	X					X	X
PVR	X					X	X
PSA	X						X
CBC /platelet count	X						
Urinalysis (dipstick)	X	X	X			X	X
Biopsy(Transrectal Ultrasound Guided - TRUS)		X					X
Prostate Volume		X					X
Antibiotic		X	X				X
Fleets Enema		X	X				
Anesthesia (periprostate block)		X	X				
onabotulinumtoxin A or saline injection via TRUS			X				
Informed Consent	X						
Antibiotic dispensing	X	X				X	
Instructions to stop alpha blocker meds 7 days prior to biopsy	X						
Drug/Placebo dispensing			X			X	
Drug/Placebo accountability						X	X
AUA Symptom score	X					X	X
BPH Impact Scale	X					X	X
Bladder Function	X					X	X
Erectile Function	X					X	X

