Mean AUA score reduction in the alpha blocker group is expected to be at most 9.6 with a standard deviation of 6.3 based on published results of a randomized trial comparing tamsulosin versus placebo.²⁹ However, that same study showed a strong pill placebo effect with a mean reduction of 5.5, resulting in a treated reduction of 4.1 above the placebo group. Another study¹³, comparing botulinum toxin to placebo, showed a mean score reduction in the botulinum group of 15.2 and no placebo change. For our study, we will assume a mean reduction of 15.2 in the onaBoNT-A group which is 9.7 more than the pill placebo effect, a mean reduction of 9.6 in the alpha blocker group and a standard deviation of 6.3 for both groups. Based on these assumptions, a sample size of 29 subjects per group will achieve 90% power to detect a difference of 5.6 with an alpha level of 0.05 using the 2-sided independent t-test. Sample size calculations were done using PASS 2008 software (Hintze, J. (2008). NCSS, LLC. Kaysville, Utah. www.ncss.com).

The drop-out rate in the alpha-blocker study was as large as 20% and our own experience with onabotulinumtoxinA (onaBoNT-A) in the MIST-2 trial has demonstrated a dropout rate of 14%. So adjusting our sample size for an expected dropout rate of 20%, we will enroll 37 patients into the onaBoNT-A and tamsulosin groups for a total of 74 patients. To address some of the problems with possible attrition bias, we will use intent to treat analysis and patients will be kept in the study as long as possible even if they are no longer on treatment. We will also compare results between the intent to treat groups and the subjects who completed treatment to determine if differences exist.

XII. RETENTION AND DROPOUT/WITHDRAWAL

Minimal dropout or loss to follow-up is expected in this cohort, especially given the short follow-up. However, if a patient drops out before 4 weeks, he will be replaced so that the required sample size is realized. For purposes of tracking the feasibility of conducting a trial of treatment with onaBoNT-A, reasons for dropout or withdrawal will be documented.

XIII. CRITERIA FOR DISCONTINUING THE STUDY

- A Subjects unable to tolerate [tamsulosin or] onaBoNT-A due to side effects.
- B Subjects can request removal from the study for any reason at any time.
- C Subjects may be withdrawn at any time at the discretion of the investigator for safety, compliance, or other reasons.

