The following events have been observed since it has been marketed: skin rash, itching, and allergic reaction. In general, these side effects occur within the first week following injection and, while usually temporary, they may last several months. Pain, tenderness, or bruising around the injection site may also occur. Local weakness of the injected muscle(s) is expected. Weakness of nearby muscles may also occur due to spread of BOTOX.

There are also possible risks of urinary retention, fecal incontinence and infection as a result of intraprostatic onabotulinumtoxinA injection.

BOTOX contains albumin, which comes from human blood. Although the blood is rigorously tested, there is an extremely remote risk for the transmission of viruses and similar infectious agents.

B Flomax®: Possible side effects of FLOMAX may include:

Flomax capsules may cause a sudden drop in blood pressure upon standing, especially after the first dose or when changing doses. Symptoms may include fainting, dizziness, and lightheadedness.

Allergic reactions may include rash, itching, and hives. Rare and more serious allergic reactions may also include swelling of face, tongue, or throat, and difficulty breathing.

Priapism (a painful erection that will not go away) may occur.

During cataract surgery, a condition called intra-operative floppy iris syndrome (IFIS) can happen if FLOMAX is being taken or has been taken in the past.

Common side effects of FLOMAX capsules may include runny nose, dizziness, and decreased semen.

Adverse experiences with Lidocaine® are, in general, dose-related and may result from high plasma levels caused by excessive dosage, rapid absorption or inadvertent intravascular injection, or may result from a hypersensitivity, idiosyncrasy or diminished tolerance on the part of the patient.

Central nervous system symptoms that may be experienced are lightheadedness, nervousness, apprehension, euphoria, confusion, dizziness, drowsiness, tinnitus, blurred or double vision, vomiting, sensations of heat, cold or numbness, twitching, tremors, convulsions, unconsciousness, respiratory depression and arrest.

Cardiovascular manifestations are usually depressant and are characterized by bradycardia, hypotension, and cardiovascular collapse, which may lead to cardiac arrest.

Allergic reactions are characterized by cutaneous lesions, urticaria, edema, or anaphylactoid reactions. These reactions to Lidocaine are extremely rare.

C Lidocaine®

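### One fixed block size of 4, printed in the protocol that blinded staff follow, makes later assignments partly predictable if the blind leaks; hidden, varying blocks are a cheap and modest improvement

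*Combined protocol and SAP*

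**What the plan says.** Section VIII.A assigns the task to the site pharmacy: "Volunteers will be randomized using a blocked randomization approach by the MEDVAMC Research Pharmacy". The scheme has one size: "Subjects will be randomized into one of the two treatment arms, using a block size of 4". It continues in the same way, since "this process is repeated for consecutive blocks of subjects until all subjects are randomized", and the section spells out the consequence: "This process ensures that after every fourth randomized subject, the number of subjects in each treatment group is equal". No stratification factor and no second block size is described. Nothing says that the size is withheld from the investigators, and it stands in the protocol they follow.

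Both arms receive an injection and a daily capsule, prepared "so that the study subject, investigator and all personnel treating or evaluating the subject will be blinded to treatment allocation". There is one site; of the volunteers, section VIII says "They are veterans who visit the MEDVAMC". Section VIII.C (Visit 3) places randomisation at the injection visit, after that day's examination and urine check. Section XV.B lists tamsulosin effects that could hint at the arm: "Common side effects of FLOMAX capsules may include runny nose, dizziness, and decreased semen". Adverse events are collected on day 3 and at week 1 after injection, and the Ejaculatory Function questionnaire at week 4.

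**The concern.** In a block known to hold two men per arm, the arms of the earlier men carry information about the later ones. Staff who read section VIII.A know where each block starts and ends, provided they keep count of randomised men. If they also form a view of what earlier men received, they have some foreknowledge of the next assignment at the point where it can still be acted on: whether, and on which day in the visit window, a man goes forward at Visit 3.

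At stake is allocation concealment. The primary endpoint is a patient-reported symptom score, and section X compares its change with an unadjusted t-test. A shift in which men enter which arm would therefore pass into the comparison without correction for baseline severity.

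**Working it through.** **Inputs.** Block size 4, two arms, 1:1 (VIII.A); 74 men (VIII, XI); assumed mean reductions 15.2 and 9.6, SD 6.3, two-sided alpha 0.05, 20% dropout (XI). The rate at which staff recognise an earlier man's arm is not in the documents, so it is varied below.

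**1. The plan's own figure.** For a difference of 15.2 − 9.6 = 5.6 and SD 6.3, the noncentral t gives 91.4% power at 29 per arm (28 gives 90.4%), so the stated 90% is met. 29 / 0.8 = 36.25, rounded up to 37 per arm, or 74. The sample size reproduces.

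**2. Worst case: every earlier arm in the block is known.** There are 6 equally likely orders of a 2:2 block.
- The fourth assignment is always certain.
- The third is certain when the first two match, with probability 2/6 = 1/3.
- Per full block: 1 + 1/3 = 4/3 certain assignments, and (4/3)/4 = 33.3%.
- 74 = 18 × 4 + 2. The last two men are the first two of an incomplete block, where nothing is certain. Expected total: 18 × 4/3 = 24, and 24/74 = 32.4%.

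**3. Partial recognition.** Let each earlier man's arm be judged correctly with probability q, independently. The chance that the best guess is right, by position in the block, is:
- first: 1/2
- second: (1 + q)/3
- third: (1 + q)/3
- fourth: q² + 2q(1 − q)²

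The block average is [1/2 + 2(1 + q)/3 + q² + 2q(1 − q)²]/4.

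| q (assumed) | fourth man | block average | certain |
|---|---|---|---|
| 0.6 | 0.552 | 53.0% | none |
| 0.7 | 0.616 | 56.2% | none |
| 0.8 | 0.704 | 60.1% | none |
| 0.9 | 0.828 | 64.9% | none |
| 1.0 | 1 | 70.8% | 33.3% |

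**4. Is the timing feasible?** Section III gives the study length as 4 years in total. If 74 men were randomised evenly over 2, 3 or 4 years (an assumption), the gap between consecutive men is 730/74 ≈ 10, 1095/74 ≈ 15 or 1460/74 ≈ 20 days. The first and fourth men of a block are three gaps apart, about 30, 44 or 59 days, so the first man's week-4 visit would usually precede the fourth man's randomisation. The third and fourth men are only 10 to 20 days apart, so the third man's week-4 data would come too late. Recognising every earlier man in time would then have to rest partly on the day 3 and week 1 calls, which is one more reason to read step 2 as an upper limit.

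**5. Effect of varying the sizes.** In a simulation of 74 men with sizes 4 and 6 mixed at random, an observer who knows both sizes and every earlier arm finds about 5.5% of assignments certain, against 32.4% with fixed 4. Best-guess accuracy falls by about 1 to 4 percentage points, depending on recognition. Adding size 2 gives about 4% certain but leaves best-guess accuracy near 70%; blocks of 2 alone give 75%.

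**The case against.** The case for leaving the scheme alone is substantial. The trial is double-dummy and randomised by the pharmacy, so nothing leaks unless the blind fails first. The clues are not specific either. Dizziness is also listed for lidocaine and Cipro (XV.C, XV.D), which men in either arm may receive. Decreased semen is listed only for tamsulosin, yet the rat data in section II describe less glandular secretion after onaBoNT-A, so the same complaint in the toxin arm is plausible. This stands, and it is why recognition well below 100% is the sensible reading.

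Four stronger readings are tempting, and the documents do not support them.
- *Blocks of 4 contradict 37 per arm.* Section VIII.A promises equality only after each fourth man, and section XI gives an enrolment target: "we will enroll 37 patients into the onaBoNT-A and tamsulosin groups for a total of 74 patients". With exactly 74 randomised, 38:36 in one direction or the other has probability 1/3, but power is 96.49% against 96.50% for 37:37. Section XII replaces men who leave before 4 weeks, so the number randomised need not be 74 at all.
- *Foreknowledge could steer the PSA judgement in exclusion criterion 19.* That rests on the screening PSA, weeks before randomisation, when a man's place in a block is unknown.
- *Foreknowledge could steer withdrawal under XIII.C.* Withdrawal follows randomisation, and a man's own side effects would prompt it under any block size.
- *Varying the blocks removes the 71% guessing accuracy.* It does not. Guessing from the running imbalance needs no block boundaries, and with perfect recognition accuracy stays near 70%.

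**Conclusion.** The point holds as an inexpensive improvement to allocation concealment. It is not an error in the plan, and no bias has been shown. A fixed, disclosed block of 4 at one site makes 32.4% of 74 assignments certain only under error-free recognition of earlier men. Under 70% to 90% recognition none is certain, and the best guess is right about 56% to 65% of the time. These figures assume independent judgements of equal accuracy on each earlier man, all available before the next man is randomised; slower or poorer recognition lowers them. The remaining route for foreknowledge is whether and when a man is randomised at Visit 3, and the window of 4 weeks after biopsy, plus or minus 3 days, narrows that too.

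**What to change.** Have the research pharmacy generate the list from permuted blocks whose size varies at random, for example 4 and 6. Avoid 2, where half of the assignments are determined by the one before. Keep the sizes in the pharmacy file only, and extend the list beyond 74 so that replacements under section XII are covered. In section VIII.A, replace the sentence "Subjects will be randomized into one of the two treatment arms, using a block size of 4" with wording such as: permuted blocks of varying size held by the pharmacy. Delete the sentence "This process ensures that after every fourth randomized subject, the number of subjects in each treatment group is equal".

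The cost is a regenerated list (only the unused part, if randomisation has begun) and a short amendment, which section XXII.E makes subject to IRB approval before it takes effect. The final split may be uneven by a few men, at most 3 if the list stops inside a block of 6, with negligible loss of power. In return, certain assignments in the worst case fall from about 32% to about 6%; the reduction in guessing accuracy is small.

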Unopened vials of BOTOX® should be stored in a refrigerator (2° to 8° C) for up to 24 months (or the expiration date on the product label). Administer BOTOX® within four hours of reconstitution and within 30 minutes of drawing into syringe; during this period the reconstituted BOTOX® should be stored in a refrigerator (2° to 8° C).

Additional BOTOX® information is available in the BOTOX® Prescribing Information package insert.

- B Tamsulosin, marketed as Flomax®, is an alpha adrenoreceptor-blocker that is used to improve symptoms associated with an enlarged prostate (BPH). It works by relaxing muscles in the bladder and prostate. This may improve urine flow rates and decrease urinary symptoms such as hesitancy and urgency.

VI PHASE OF STUDY Phase 2

VII ELIGIBILITY CRITERIA

A Inclusion

- 1 Males at least 50 years of age
- 2 AUA Symptom Score greater than 8
- 3 Voided volume greater than 125 ml
- 4 Maximum urinary flowrate less than 15 ml/sec.
- 5 Must agree to all procedures and willfully consented

B Exclusion

- 1 Any prior surgical intervention or use of 5-alpha reductase medical treatment for BPH
- 2 Current diagnosis of acute or chronic prostatitis (which may cause LUTS that mimic BPH)
- 3 Previous exposure to onabotulinumtoxinA
- 4 Overactive bladder without obstructive symptoms (i.e. decrease in force of stream, hesitancy, intermittency, post-void dribbling);
- 5 Active urinary tract disease or biopsy of the prostate within the past 6 weeks;
- 6 Two documented urinary tract infections of any type in the past year (UTI defined as greater than 100,000 colonies per ml urine from midstream clean catch or catheterized specimen)
- 7 Uncontrolled diabetes
- 8 History of bladder calculi (stones)
- 9 Penile prosthesis or artificial urinary sphincter [placement]
- 10 Documented bacterial or acute prostatitis within the past year
- 11 Episode of unstable angina pectoris, myocardial infarction, transient ischemic attack, or cerebrovascular accident (stroke) within the past 6 months
- 12 Known primary neurologic conditions such as multiple sclerosis, myasthenia gravis or Parkinson's disease, or other neurological diseases known to affect bladder function
- 13 History or current evidence of carcinoma of the prostate or bladder, pelvic radiation or surgery, urethral stricture, or bladder neck obstruction

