Ejaculatory Function	X					X	X
Adverse Events			X	X	X	X	X
Concomitant Meds	X	X	X	X	X	X	X

C Procedures

1 Visit 1: Screening

- Informed consent will be obtained prior to any research-related procedures.
- A physical including a digital rectal exam (DRE) will be performed.
- The subject's medical history and concomitant medications will be discussed and documented.
- The subject's vital signs will be taken and documented.
- The subject will complete the following questionnaires:
 - The AUA symptom score
 - BPH Impact Scale

- Bladder Function
- Erectile Function
- Ejaculatory Function
- The subject will undergo uroflow testing and will provide a post-void residual urine measurement.
- Blood (about 10 ccs or 2 teaspoons) will be drawn for CBC with platelets and PSA testing.
- A urinalysis (dipstick) will be performed.
- Dispense a Bactrim DS (antibiotic) 160/800mg tablet orally twice a day [Cipro (generic is permissible) 500 mg twice a day] with instructions to take for 1 day prior to biopsy, day of biopsy, and for 1 day following biopsy (total of 3 days).
- Subjects will be instructed to stop taking alpha blocker medications 7 days prior to biopsy.

2 Visit 2: Biopsy

- The subject's concomitant medications will be discussed and documented.
- The subject's vital signs will be taken and documented.
- A urinalysis (dipstick) will be performed to ensure that no infection is noted or suspected.
- Dispense an antibiotic
- Prostate size is measured via transrectal ultrasound on patients after receiving a Fleet's enema the morning of the examination.
- Transition zone biopsies will be performed.

3 Visit 3: Injection (4 weeks post-biopsy, ± 3 days)

- The subject's concomitant medications will be discussed and documented.
- The subject's vital signs will be taken and documented.
- Any adverse events experienced by the subject will be documented.
- **Injection Procedures:** onaBoNT-A solution does not contain a preservative, it should be administered within 4 hours after reconstitution and within 30 minutes of drawing into the syringe. The drug should be stored in a refrigerator when not in use during this period.
 - **Patient Preparation**
 - a. Patient is examined and submits urine for urinalysis which is examined by standard dipstick analysis or microscopic examination prior to randomization and preparing onaBoNT-A solution to ensure that no infection is noted or suspected.

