- C Urine specimens collected for dipstick analysis during the screening visit are routine for patients with BPH and LUTS and will be handled according to standard of practice. The test results will be included in the subject's research and medical charts.

X. STATISTICAL ANALYSIS

The primary endpoint, change in AUASS score from baseline to 3 months, between the onaBoNT-A and tamsulosin groups will be analyzed using the 2-sided independent t-test.

Baseline measures of the data such as age and ethnicity as well as secondary endpoints will be examined using summary statistics to determine if any differences exist between the 2 study groups.

Graphical methods will be used to access distributional properties of the secondary endpoints (urinary flow rate, serum PSA, prostate volume symptom relief, post-void residual, BPH impact score, Bladder Function, Erectile Function and Ejaculatory Function questionnaires). If extreme departures from normality are found, use of non-parametric analytical methods such as the Wilcoxon rank-sum test or transformation of the data will be considered. Questionnaire scores will be examined for reliability using Cronbach's alpha. The distributions of the scores will be examined to see if they are evenly distributed around the mid-point of the scales or are clustered at the top or bottom of the scales (ceiling or floor effect). If strong ceiling or floor effects are found, this could limit the usefulness of these measures. Changes in these secondary endpoints will be assessed using either the independent t-test or its non-parametric equivalent, the Wilcoxon rank sum-test. Statistical analysis will be done using SAS, version 9.2 (SAS Institute, Cary NC).

The endpoints apoptotic index, proliferation index, nerve density, stromal reactive indexes, and vessel density, will be checked for their distributional properties using the methods described for the data collected in Aim 1. Change from baseline to 3 months will be analyzed using either the 2 sided t-test or the Wilcoxon rank sum test.

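### The only pre-treatment AUASS is taken at Visit 1, possibly on alpha-blocker for some men, and the unadjusted t-test on change uses neither baseline AUASS nor prior use

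*Combined protocol and SAP*

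**What the plan says.** Section X (Statistical Analysis) defines "The primary endpoint, change in AUASS score from baseline to 3 months" and compares the arms with a two-sided independent t-test. It does not name the baseline visit and includes no covariate. Section XIV (Data Analysis) lists other tests, also without covariates.

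The Schedule of Events (Section VIII.B) and the visit lists (VIII.C) place the AUASS at Visits 1, 6 and 7 only. The BPH Impact Scale, the other questionnaires, flow rate and PVR follow the same pattern. None is taken at Visit 2 (biopsy) or Visit 3 (injection). Randomisation belongs to Visit 3, where the patient "submits urine for urinalysis which is examined by standard dipstick analysis or microscopic examination prior to randomization".

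On alpha-blockers, the Visit 1 procedures state that "Subjects will be instructed to stop taking alpha blocker medications 7 days prior to biopsy", and the schedule has a matching row, "Instructions to stop alpha blocker meds 7 days prior to biopsy". Exclusion 20 (Section VII.B) reads "No alpha-blockers in the past 7 days before biopsy". Exclusion 1 bars "Any prior surgical intervention or use of 5-alpha reductase medical treatment for BPH" and does not mention alpha-blockers. Entry requires "AUA Symptom Score greater than 8". At Visit 1, "The subject's medical history and concomitant medications will be discussed and documented", so alpha-blocker use at screening is already recorded.

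**The concern.** A man taking an alpha-blocker at Visit 1 can complete his only pre-treatment AUASS on drug and be told at that same visit to stop before the biopsy. A man not taking one completes it untreated. Both scores serve as baseline for the same endpoint.

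The comparator is itself an alpha-blocker, so this affects what change means. For a user randomised to tamsulosin, change may run from on-alpha-blocker to on-tamsulosin. For a non-user it runs from untreated to treated. Section XI plans on mean reductions of 15.2 and 9.6 points, and the observed arm means could not be read against those figures without knowing how many men were on drug at Visit 1.

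The mixture also adds variance to the change score. The planned test does not remove it, although the variable needed to do so is on the case report form.

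**Working it through.** **Inputs from Section XI.** Difference 5.6, SD of change 6.3 in both arms, two-sided alpha 0.05, 29 per arm for 90% power, 20% dropout, 37 enrolled per arm. Tamsulosin effect over placebo: 9.6 − 5.5 = 4.1 points. Dropout in the sponsor's own earlier trial of the toxin: 14%.

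**The plan's own figure.** Noncentral-t power with difference 5.6 and SD 6.3 is 90.4% at 28 per arm and 91.4% at 29, so the stated 29 is sound. 29/0.80 = 36.25, rounded up to 37 per arm and 74 in total, which matches.

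**Age of the score.** A user stops at least 7 days before biopsy, and injection is 4 weeks ± 3 days after biopsy (25 to 31 days). His on-drug score is at least 7 + 25 = 32 days old at randomisation.

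**Assumptions.** The documents give no share q of users at Visit 1, so q is taken from 0 to 75%. On-drug scores are taken to be lower by a constant d. One value is d = 4.1, the drug-over-placebo effect above. The other is d = 2.0, about half, because men who still score above 8 on drug may have responded less.

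**Formulas.**
- Understatement of mean change in each arm = q·d
- SD of change = √(6.3² + q(1−q)d²)
- Power from the noncentral t, difference 5.6

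Example with q = 0.5 and d = 4.1: the shift is 2.05 and SD = √(39.69 + 0.25 × 16.81) = √43.89 = 6.63.

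| d | q | Shift per arm | SD | Power, 29/arm | Power, 32/arm | Power, 37/arm |
|---|---|---|---|---|---|---|
| – | 0 | 0 | 6.30 | 91.4% | 93.8% | 96.5% |
| 4.1 | 0.10 | 0.41 | 6.42 | 90.4% | 93.0% | 95.9% |
| 4.1 | 0.25 | 1.02 | 6.55 | 89.3% | 92.1% | 95.3% |
| 4.1 | 0.50 | 2.05 | 6.63 | 88.6% | 91.4% | 94.8% |
| 4.1 | 0.75 | 3.07 | 6.55 | 89.3% | 92.1% | 95.3% |
| 2.0 | 0.50 | 1.00 | 6.38 | 90.7% | 93.3% | 96.1% |

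The 32 per arm is 37 × 0.86 = 31.8, from the 14% dropout. In the worst row the 95% CI half-width at 29 per arm goes from 3.31 to 3.49. Chance imbalance in prior use has a standard error of 4.1 × √(2 × 0.25/29) = 0.54 points on the arm difference. That is the same extra variance seen another way, not a further loss.

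**What adjustment recovers.** Simulation with 8,000 runs, d = 4.1, q = 0.5 and 29 per arm:
- t-test on change from Visit 1: power 88.8%, type I error 5.0%
- with prior use as covariate: 91.3%, type I error 5.3%
- change from a Visit 3 score assumed to be off-drug: 91.8%, type I error 5.1%

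At 37 per arm the powers are 94.8%, 96.4% and 96.6%. The Monte Carlo standard error is about 0.3 percentage points, so the last two methods cannot be told apart on precision. Any further gain from adjusting for baseline AUASS is not quantified, because the documents give neither a baseline SD nor a correlation.

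**The case against.** The case on the other side is substantial, and most of it stands.

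- **A mixed baseline is permitted, not stated.** No text says that any enrolled man is on drug at Visit 1. Section III describes the treatments as frontline therapy, which points towards a largely untreated cohort. The background's first-line recommendation and recruitment from a urology clinic (Section XXII.B) point the other way. Neither gives a prevalence, and no criterion enforces an untreated cohort. The point is therefore conditional.
- **A reader might infer that the arm comparison is biased against tamsulosin.** It is not. The Visit 1 score precedes randomisation, so any offset has the same expectation in both arms and cancels in the difference. The primary test is between arms, and no within-arm hypothesis is tested.
- **A reader might infer that the endpoint cannot be computed because baseline is undefined.** Only one pre-treatment score exists, so it can. What is missing is one sentence.
- **A reader might infer that the trial is underpowered.** The table does not show that. Using 9.6 as the offset would give 75.4% at 29 per arm with 50% users, but 9.6 includes the 5.5-point placebo response and is not a drug effect.
- **The net error in mean change is not known.** Regression to the mean from the eligibility score inflates apparent improvement, and an on-drug baseline shrinks it. The shifts in the table are only the second part.

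What remains is that the test ignores two recorded pre-randomisation variables, one of which may define two different starting states.

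**Conclusion.** The concern holds in a limited form and is minor to moderate. The timing of the only pre-treatment AUASS, the stop instruction given at that visit and the lack of any bar on current users together allow a baseline that mixes treated and untreated men. The planned test does not account for it.

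The between-arm difference stays unbiased and type I error stays near 5%. Under an assumed 0 to 75% users and a constant 4.1-point offset, each arm's mean change is understated by 0 to 3.1 points from this source. Power is no lower than 88.6% at 29 per arm and at least 94.8% at 37. With a 2.0-point offset, power at 29 per arm is at least 90.7%. If no user enrols, the mixture costs nothing. The user share and the offset in this population are assumptions, and the main consequence is for interpreting change within arms.

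**What to change.** **Main change, text only.** State that baseline is the Visit 1 score. Replace the t-test with ANCOVA of 3-month AUASS on arm, baseline AUASS and alpha-blocker use at screening (yes/no, from the concomitant-medication record). The cost is one sentence on baseline and one on the model, with no new data. This recovers nearly all the lost precision but does not create a common starting state.

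**Optional addition, for interpretation.** Repeat the AUASS and the other Visit 1 questionnaires at Visit 3, before randomisation. If the Visit 3 score is used as baseline, apply it to all the questionnaire endpoints and keep Visit 1 scores for eligibility. The cost is a few minutes at an existing visit. Flow rate and PVR would still have a Visit 1 baseline, and arm means would also shift because some regression to the mean from the eligibility score is removed.

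**Clarification needed.** Exclusion 20 and the Visit 1 instruction cover the 7 days before biopsy, but both are silent on alpha-blocker use between biopsy and injection. The sponsor should reconcile these passages with the Visit 3 procedures. Until then a Visit 3 score is not assured to be off-drug, so the optional addition should not be presented as delivering an untreated baseline.
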